# Stored Plasma for HCV Studies

Plasma samples will be collected and stored for potential HCV sequencing and other virology studies. For processing and shipping instructions, refer to the A5348 LPC.

## Plasma HIV-1 RNA (real time)

A screening plasma HIV-1 RNA level must be obtained within 42 days prior to study entry, using an FDA-approved assay from any laboratory or clinic that has a CLIA certification or its equivalent. On-study HIV-1 RNA should be performed at the designated testing laboratory and is only required for participants taking ARV. Refer to the A5348 LPC for processing and shipping information.

Participants on ARV who later experience HIV-1 VF while on HIV therapy should be managed as per section 7.1.6.

## Plasma HIV-1 Resistance Testing (real-time)

If there is a confirmed HIV-1 VF (HIV-1 VL  $\geq$ 200 copies) in a participant while taking HCV treatment (or within 4 weeks after permanent discontinuation), a plasma specimen must be obtained at the time of the confirmation sample and, if HIV-1 VF is confirmed with an HIV-1 VL  $\geq$ 200, the sample must be sent to A5348 testing lab as per the LPC for evidence of drug resistance.

6.3.9 Immunologic Studies

#### CD4+/CD8+ T-cells

Screening CD4+/CD8+ testing may be done by any laboratory or clinic that possesses a CLIA certification or its equivalent.

During the study, all laboratories must possess a CLIA certification or its equivalent and must be certified for protocol testing by the DAIDS Immunology Quality Assurance (IQA) Program.

6.3.10 Additional Stored Samples

Plasma will be collected and stored at the indicated visit (see section 6.1) for future testing including HCV and HIV resistance testing, HCV genotype confirmation if necessary, as well as future ACTG-approved research, and shipped according to the A5348 LPC. Plasma will be collected from all participants for HIV and /or HCV resistance testing, should virologic breakthrough occur. Participants will be asked to provide consent for use of stored specimens for future research.

There will be a one-time collection of whole blood for future genetic analyses for participants who consent to this sample collection.

## Stored Urine

Urine will be collected and stored for evaluation of retinol binding protein, beta-2 microglobulin, and creatinine. Refer to A5348 LPC for instructions.

## 6.3.11 Tenofovir PK Samples

The tenofovir (TFV) PK sampling evaluations will be only required for the first 15 participants, and consenting participants thereafter, who are taking ritonavirboosted protease inhibitor and tenofovir.

The first TFV PK evaluation will occur at entry prior to initiation of LDV/SOF. For the entry evaluation, the date and time of the last three doses of TFV and other ARVs

must be recorded on the CRF. The participant will not receive study treatment until after all of the PK samples have been obtained. The second TFV PK evaluation will occur 4 weeks after initiating LDV/SOF. For the week 4 evaluation, the date and time of the reference (current) dose and the last three doses of LDV/SOF and the last three doses of ARVs taken immediately prior to the predose blood sample must be recorded on the CRF.

Weight will also be recorded on the CRF.

For these visits, participants will come in to the clinic approximately 24 hours after their previous dose of TDF, following an 8 hour fast. A blood sample will be obtained at pre-dose, participants will then take an observed dose of TDF (and LDV/SOF at week 4 only), and additional blood samples will be obtained at 1 and 4 hours post-observed dose. Participants should be fasting until after the 1-hour blood draw has been completed. After this draw, participants may eat and no specific meal is required.

If the participant is not fasting at the entry visit, all entry evaluations should be performed except for the tenofovir PK evaluation and the participant should return fasting within 48 hours and before administration of study drug for the tenofovir PK evaluation.

Participants will be instructed to keep a written record of the date and time of the last three doses of all HIV-1 and HCV drugs taken prior to the PK visit in the medication diary (see section 6.3.17), and to bring this information to the clinic.

The week 4 evaluation should be rescheduled if participants are not considered to be at steady-state due to missed doses of any ARV or DAA (for the week 4 PK visit, excluding ribavirin) within the previous 3 days.

Refer to section 10.2 for more detail on PK plan. For processing and shipping instructions, refer to the A5348 LPC.

6.3.12 Dried blood spots (DBS)

One DBS will be collected on ALL participants at required visits regardless of ARV regimen, as outlined in section 6.1 to evaluate SOF and LDV blood levels, as well as potentially to evaluate tenofovir levels and for other future research evaluations in participants who have provided consent for this. The date and time of the most recent LDV/SOF and ARV dose will be recorded on the CRF.

For processing and shipping instructions, refer to the A5348 LPC.

6.3.13 IL-28B genotype

IL-28B genotype will be conducted at entry, if no record of prior IL-28B testing is available. Testing can be conducted locally at a CLIA-certified laboratory. If not available to sites as local standard of care test, IL-28B testing may be conducted centrally, as outlined in the A5348 LPC.

6.3.14 Pregnancy Prevention Counseling

Counseling on pregnancy prevention will be conducted as per site's standard of care per the SOE. This will not be recorded on the CRF.

6.3.15 Adherence Assessment

Adherence assessment is performed for study treatment only.

This study will use a combination of three measures of adherence (1) the Adult ACTG 4-day recall, (2) pill count, and (3) LDV and SOF metabolite concentrations through collection of dried blood spots (DBS).

6.3.16 Study Drug Dispensing

Participants must be instructed to bring back all bottles of study drugs in the original container at the post-entry study visits.

6.3.17 Medication Diary

The medication diary will be distributed and collected as per the SOE. The diary is recommended to be used to record dosing for the three doses of HCV and HIV medications prior to the two tenofovir PK visits. They may be used as an optional tool for participants to record medication adherence throughout the study and for recall at the time of the DBS blood draws. A sample medication diary is provided for use on the DMC website (http://www.fstrf.org), but sites may choose to use a site-provided diary.

#### 7.0 CLINICAL MANAGEMENT ISSUES

Criteria for participant management, dose interruptions, dose adjustments and discontinuation, or changes in treatment will be described only for toxicities attributable to study drugs (i.e., SOF, LDV, and RBV).

The grading system for drug toxicities is located in the DAIDS Table for Grading the Severity of Adult and Pediatric Adverse Events (DAIDS AE Grading Table), Version 2.0, November 2014, which can be found on the DAIDS RSC Web site: http://rsc.tech-res.com/safetyandpharmacovigilance/gradingtables.aspx.

NOTE: The team must be notified via e-mail within 72 hours regarding toxicities that result in a change in study regimen ([contact]).

#### 7.1 Toxicity

Toxicity management is the responsibility of the site investigator who is encouraged to communicate with the core team regarding any management questions.

7.1.1 Management of Side Effects of RBV (Arm A only)

The most common AE of RBV therapy is anemia due to hemolysis. Anemia typically occurs within 1 to 2 weeks of initiating RBV therapy and usually resolves within 4 to 8 weeks of drug discontinuation or dose reduction. Indirect bilirubin elevation is commonly seen in those participants with anemia secondary to RBV-induced hemolysis.

Another major side effect of RBV is its teratogenicity; therefore pregnant women or breastfeeding women and men with pregnant sexual partners should not receive RBV. Women who become pregnant on study and men on study whose partners become pregnant must discontinue study treatment and will be managed per section 7.2.

RBV dosing in this study will be based on weight at study entry (see section 5.0). Dose reduction of RBV is the recommended management for RBV associated anemia and should be performed according to the product label. Information is summarized in Table 7-1 It is recommended that sites contact the protocol core team with questions regarding difficult anemia management and/or if it is felt RBV discontinuation is required. Participants may continue to take LDV/SOF if RBV is temporarily or permanently discontinued.

## Table 7-1: Suggested RBV Dose Reduction in the Event of Anemia

Laboratory Values	Reduce RBV Dose to 600 mg/day if:	HOLD RBV if:				
Hemoglobin in participants with no cardiac disease	<10 g/dL	<8.0 g/dL				
Hemoglobin in participants with history of stable cardiac disease	≥2 g/dL decrease in hemoglobin during any 4 week period treatment	<10 g/dL despite 4 weeks at reduced dose				
Symptomatic drop in hemoglobin to be managed at the discretion of the site investigator and can be discussed with the protocol chairs.						

## Reintroduction of RBV

If RBV is temporarily stopped due to anemia, the hemoglobin must be rechecked within 2 weeks and at 2-week intervals until stable. Once RBV has been withheld due to either a laboratory abnormality or clinical manifestation, an attempt may be made to restart RBV at 600 mg daily in two divided doses and further increase the dose to 800 mg daily in two divided doses. However, it is not recommended that RBV be increased to the original assigned dose. Please refer to the table below for dosing intervals.

Table 7-2: Suggested RBV Dosing Intervals for Reintroduction

Daily	Morning	Evening Dose
Dose	Dose	
600 mg	400 mg (2	200 mg (1 tablet)
	tablets)	
800 mg	400 mg (2 tablets)	400 mg (2 tablets)

NOTE A: The half-life of RBV in participants with normal renal function is 290 hours.

NOTE B: The ranges of hemoglobin values used as criteria for triggering dose reduction of RBV do not correspond to those used to grade toxicities in the DAIDS Table for Grading the Severity of Adult and Pediatric Adverse Events, Version 2.0, November 2014. Therefore, sites are expected to use A5348-specific criteria.

7.1.2 Management of Side Effects of LDV/SOF

Dose reduction of LDV/SOF will not be allowed in the study. If LDV/SOF is stopped for toxicity, it should not be restarted and the participant should complete the treatment discontinuation visit. All participants must complete the week R+4, R+12, and R+24 visits. The week R+4, R+12, and R+24 visits will be scheduled from the date of the last dose of study treatment.

If LDV/SOF is discontinued, Arm A participants should discontinue RBV. Under no condition should the participant remain on RBV monotherapy.

Participants who meet any of the following laboratory criteria should stop treatment with LDV/SOF and RBV:

- ALT or AST ≥10 x ULN (see section 7.1.5 for additional detail on elevated transaminases)
- Confirmed direct bilirubin 3 x ULN and > 2.0 mg/dL
- Any Grade 3 or greater rash associated with constitutional symptoms
- Any Grade 4 event assessed as related to treatment with LDV/SOF
- 7.1.3 Specific Guidance for Creatinine Clearance (CrCl)

CrCl will be calculated throughout the study using Cockcroft-Gault method. Refer to the Cockcroft-Gault calculator located on the FSTRF web site and using the weight obtained at each visit.

- 7.1.3.1 If a participant experiences a CrCl decrease to <50 mL/min or an increase in creatinine of ≥ 0.4 mg/dL from entry creatinine, the following evaluations should occur:
  - Within 7 days: repeat evaluation of electrolytes, creatinine, serum phosphorus, urinalysis including assessment of proteinuria and glucosuria with spot creatinine and protein assessment and calculation of protein/creatinine ratio.
  - Assessment of current weight for repeat CrCl calculation.

If calculated CrCl is confirmed to have decreased to <50 mL/min, the A5348 protocol core team should be contacted by e-mail at [contact].

 Medical evaluation must include a full review of current medications, including those taken on an as-needed basis, those which are sold over the counter, and any dietary and herbal supplements. Study DAAs may be continued. Ribavirin should be dose reduced for CrCl < 50 as follows:
 Table 7-3: Suggested Dose Reduction of Ribavirin

Creatinine 30-50	Ribavirin Dose 200 mg every other day alternating with 400 mg every other day
< 30	200 mg daily and consider discontinuation

- Creatinine and chemistries should be repeated as clinically indicated until resolution.
- If CrCl does not improve in the subsequent two scheduled study visits (two CrCl values still <50 mL/min) then consideration of discontinuation of all potentially nephrotoxic medications including potentially nephrotoxic ARV including tenofovir must be undertaken in consultation with the treating provider.
- Changes to the ARV regimen require notification of the A5348 protocol core team by e-mail at [contact]. Please refer to section 7.1.6 for guidance regarding changes in ARV.
- Continue further medical management as appropriate.
- If CrCl improves, consideration must be given to the readjustment of any dose modifications that have been made.
- 7.1.3.2 CrCl value <30 mL/min: This should be handled on a case by case basis. The site should notify the core team of all participants with a confirmed CrCl <30 mL/min.
- 7.1.4 Specific Guidance for New or Worsening Proteinuria or Glucosuria

Participant who develop new proteinuria or glucosuria (1+ or greater) or an increase in glucosuria or proteinuria of  $\geq$ 1+ from baseline should have the following evaluations occur:

- Within 7 days, repeat urinalysis with spot protein and creatinine, calculation of protein/creatinine ratio, repeat serum chemistry, creatinine and phosphate.
- Medical evaluation must include a full review of current medications, including those taken on an as needed basis, those which are sold over the counter, and any dietary and herbal supplements, as well as assessments for causes of proteinuria and/or glucosuria including concomitant disease processes such as diabetes and toxicity from current medications including HCV treatment. Sites are welcome to consult with the core team with any questions or concerns regarding management [contact].

If new or worsened proteinuria and/or glucosuria are confirmed, the study team should be notified. Urinalysis should be repeated as per the SOE and more frequently if clinically indicated.

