NOTE: Inability to definitively determine genotype or a non-GT-1 will exclude the participant from study participation.

4.1.8 Prior virologic treatment failure with SOF-containing regimen (SOF/RBV, SOF/PEG/RBV, and SOF/SIM).

NOTE A: See section 6.3.3 for requirements for documentation of prior HCV treatment and response.

NOTE B: Prior virologic failure is defined as quantifiable HCV RNA at any time after receiving HCV therapy as prescribed that was not attributed to reinfection.

NOTE C: HCV reinfection is defined by (1) documentation of clearance of prior infection (as evidenced by prior positive anti-HCV Ab or HCV RNA) either spontaneously or after treatment with two negative HCV RNA a minimum of 3 months apart AND (2) positive HCV RNA after documentation of two negative HCV RNA obtained a minimum of 3 months apart *or* infection with a different HCV genotype from the prior infection.

4.1.9 Body mass index (BMI)  $\geq$  18 kg/m^2 within 42 days prior to study entry.

NOTE A: A BMI calculator is available at the DMC website (http://www.fstrf.org).

NOTE B: The height and weight measurement used to calculate BMI must be obtained on the same day.

- 4.1.10 The following laboratory values obtained within 42 days prior to study entry by any US laboratory that has a CLIA certification or its equivalent.
  - HCV RNA  $\geq 10^4$  IU/mL
  - Hemoglobin  $\geq$  12.0 g/dL for male,  $\geq$ 11.0 g/dL for female participants
  - Platelets  $\geq$  50,000/mm^3
  - International normalized ratio (INR) ≤1.5 x ULN unless participant has known hemophilia or is stable on an anticoagulant regimen affecting INR, in which case any INR value is acceptable
  - Albumin ≥ 3.0 g/dL
  - Creatinine clearance (CrCl) ≥ 60 mL/min, as calculated by the Cockcroft-Gault equation (refer to section 6.3.5 for calculator utility link)
  - Aspartate aminotransferase (AST) (SGOT) < 10 x ULN
  - Alanine aminotransferase (ALT) (SGOT) < 10 x ULN
  - Direct bilirubin  $\leq 1.5 \times \text{ULN}$
  - Hgb A1C ≤ 8.5%
- 4.1.11 Screening electrocardiogram (ECG) without clinically significant abnormalities as determined by the investigator within 42 days prior to study entry.
- 4.1.12 Willing and able to provide written informed consent.

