### 7.1.5 Specific Guidance for Transaminase Elevations

If a participant experiences an ALT level  $\ge 5 \times ULN$  that is  $\ge 2 \times Baseline$ , a confirmatory test must be performed within 72 hours. If the ALT is confirmed  $\ge 5 \times ULN$ , the management guidelines in Table 7-4 must be followed.

If a participant experiences an increase in ALT by one or more toxicity grades compared to the previous nadir (for example, ALT Grade 0 at nadir increases to Grade 1 or above, or ALT Grade 1 at nadir increases to Grade 2 or above), safety laboratory assessments and clinical evaluation of the participant should be conducted within 1 week.

Alternative management of ALT increases requires approval from the A5348 protocol core team by email at [contact].

ALT ≥10 x ULN	Permanently discontinue study drugs. Evaluate and manage the participant as medically appropriate.
ALT > 5 x ULN and >2 x baseline	Evaluate and manage the participant as medically appropriate. Continue study drugs and repeat liver function tests within 3 days and as clinically indicated until resolution. Perform clinical assessment within 1 week. If ALT values during follow-up are increased >2-fold from the prior values, then permanently discontinue study drugs.

Table 7-4: Management of Confirmed ALT Levels  $\geq 5 \times ULN$  and  $\geq 2 \times Baseline$ 

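### A first ALT of 10 x ULN or more that repeats at 5 to <10 x ULN and >2 x baseline: Protocol 7.1.2 ends treatment for good, while Table 7-4 says continue

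*Protocol*

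**What the plan says.** **Section 7.1.2 (side effects of LDV/SOF).** The first laboratory stopping criterion for LDV/SOF and RBV is "ALT or AST ≥10 x ULN (see section 7.1.5 for additional detail on elevated transaminases"). The next one is "Confirmed direct bilirubin 3 x ULN and > 2.0 mg/dL", so a confirmation requirement is written for bilirubin and not for transaminases. The same section states: "If LDV/SOF is stopped for toxicity, it should not be restarted".

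**Section 7.1.5 (transaminase elevations).** When ALT is at least 5 x ULN and at least 2 x baseline, "a confirmatory test must be performed within 72 hours". This trigger has no upper limit. If ALT is confirmed at 5 x ULN or more, "the management guidelines in Table 7-4 must be followed". Table 7-4 is titled for confirmed ALT levels. Row 1 (ALT at least 10 x ULN) ends treatment permanently. Row 2 (at least 5 x ULN and more than 2 x baseline) says: "Continue study drugs and repeat liver function tests within 3 days and as clinically indicated until resolution". Row 2 then requires a permanent stop if ALT more than doubles from the prior value. For departures from these rules, "Alternative management of ALT increases requires approval from the A5348 protocol core team".

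**Related rules.** Section 4.1.10 admits a baseline ALT below 10 x ULN. Section 8.1 ends treatment after seven consecutive missed doses.

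**The concern.** The two sections give opposite default orders for the same participant when a first ALT reaches 10 x ULN and the repeat is lower but still raised. One order cannot be undone.

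Under the 7.1.2 wording, a potentially curative course ends on a value that did not repeat at that level. If a site instead waits for the repeat, as 7.1.5 allows, the participant may keep dosing for up to 72 hours at a level where both sections end treatment once it is confirmed. Nothing tells the site which to do in that interval. Sites could act differently unless each asks the core team. The stake is individual safety and treatment completion.

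**Working it through.** No sample-size or power figure applies, so the check compares the two rules directly. All ALT values are in multiples of ULN: b is baseline, f the first value, r the repeat.

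**1. Conditions**

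| Rule | Condition | Action |
|---|---|---|
| 7.1.2 | f ≥ 10 | stop, no restart of LDV/SOF |
| 7.1.5 repeat | f ≥ 5 and f ≥ 2b | repeat within 72 hours |
| Table 7-4 row 1 | r ≥ 10 | permanent stop |
| Table 7-4 row 2 | r ≥ 5 and r > 2b | continue |

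The table is entered here with r, because its title refers to confirmed levels.

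**2. Can the conflict occur?** It needs f ≥ 10, 5 ≤ r < 10 and r > 2b. From r < 10 and r > 2b, b < 10/2 = 5, which 4.1.10 allows. Then f ≥ 10 > 2b, so the repeat is always required. With b = 1, f = 12, r = 8: 12 ≥ 10 gives stop under 7.1.2; 8 ≥ 5 and 8 > 2 gives continue under row 2.

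**3. Grid check.** In steps of 0.5, with b from 0.5 to 9.5 (19 values), f from 10 to 20 (21) and r from 5 to 9.5 (10), there are 19 x 21 x 10 = 3990 combinations. Of these, 1365 meet both the stop rule and row 2, and all 1365 trigger the repeat. This shows that the conflict is reachable. It is not a probability.

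**4. Where there is no conflict**
- f ≥ 10 and r ≥ 10: both sections stop.
- AST ≥ 10: 7.1.5 has no AST rule, so 7.1.2 alone applies and says stop.
- f ≥ 10 but f < 2b: this needs b > 5 (for b = 6, f from 10 to <12). 7.1.5 requires no confirmatory test, and 7.1.2 alone says stop.
- r < 5: 7.1.5 gives no dosing instruction, so this is a gap and not an opposing order.

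**5. Size per affected participant.** Planned LDV/SOF doses are 12 x 7 = 84 in Arm A and 24 x 7 = 168 in Arm B.

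| | Arm A | Arm B |
|---|---|---|
| 72-hour hold | 3/84 = 3.6% | 3/168 = 1.8% |
| Permanent stop at week 1 | 77/84 = 91.7% | 161/168 = 95.8% |
| Permanent stop at week 8 (A) or week 20 (B) | 28/84 = 33.3% | 28/168 = 16.7% |

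Three missed doses are below the seven-dose limit in 8.1.

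**6. How many participants?** The documents give no rate for ALT ≥ 10 x ULN. Section 2.3.15 names lipase (1.7%) and glucose (1.5%) as the most common Grade 3 or 4 chemistry abnormalities in the Phase III studies. Assume that ALT counts as chemistry, that 10 x ULN is at least Grade 3, and that those mono-infected participants are a fair guide. The rate is then at most about 1.5%, or 0 to 0.015 x 40 = 0.6 of the planned sample and 0 to 0.015 x 7 = 0.1 of those enrolled. Only those whose repeat falls into row 2 meet the conflict.

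**The case against.** The best defence is the cross-reference. The 7.1.2 bullet points to 7.1.5, whose title announces specific guidance on transaminases, so a site may reasonably take the confirmation step from there. Another reading is that confirmation at 5 x ULN opens the table and the first value then selects row 1. Both are arguable, but they lead to opposite actions and neither is written. The text does not say which value governs or what to do about dosing meanwhile. The core-team route permits exceptions but does not set the default.

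Two broader criticisms do not stand. A reader might infer that stopping on a single AST value is also an error. It is one clear, conservative instruction, and the rash and Grade 4 criteria in 7.1.2 carry no confirmation step either. A reader might also see a contradiction for a high-baseline ALT below 2 x baseline. There is none, because only 7.1.2 speaks to it. It matters only for the fix: once confirmation is required in 7.1.2, this case needs a repeat rule too.

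The defence is also right that a loosely drafted remedy would cause trouble. The related-Grade-4 stop in 7.1.2 could still apply to the same ALT value, holds could recur, and the RBV reintroduction advice in 7.1.1 could leave a participant on 600 mg (60% of 1000 mg or 50% of 1200 mg).

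**Conclusion.** Wrong as written, at the lowest severity. For a first ALT of at least 10 x ULN that repeats at 5 to <10 x ULN and above 2 x baseline, the literal text orders both a permanent stop and continuation, and it is silent on dosing before the repeat. This rests on reading the 7.1.2 bullet as worded and on entering Table 7-4 with the confirmed value, as its title indicates.

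A reader might infer that the primary results are at risk. The documents do not support that: the event is expected to be rare, SAP Version 2.0 reports early closure with 7 participants and a descriptive report, and few if any participants would be affected. The point is about clear safety instructions.

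**What to change.** Split the first 7.1.2 bullet.

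- **AST ≥10 x ULN:** unchanged.
- **Confirmed ALT ≥10 x ULN:** on a first ALT at this level, whatever the baseline, hold LDV/SOF and RBV together and repeat within 72 hours.
  - Repeat ≥10 x ULN: stop permanently.
  - Repeat <10 x ULN: resume the prior doses and monitor as in Table 7-4 row 2.
  - The hold is not a toxicity stop under the no-restart rule and does not trigger the RBV reintroduction step.
  - Any later ALT ≥10 x ULN stops treatment permanently, without a second hold.
  - An isolated ALT value falls under this bullet and not the Grade 4 bullet.
  - If no repeat is available by 72 hours, keep holding and contact the core team.

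In 7.1.5, add that the repeat value selects the row of Table 7-4, and that study drugs are held as in 7.1.2 after a first value ≥10 x ULN. Leave the Table 7-4 title unchanged.

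A hold is preferred to continued dosing because both sections end treatment at this level once it is confirmed. The cost per affected participant is about 3 daily doses, plus one extra blood draw for a high-baseline ALT. The change needs a clarification memo or a letter of amendment, which may require IRB/EC approval. Scheduled visits, sample size and analysis do not change.
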